11.4. Determination of Sample Size

Estimation of sample size is based on the primary efficacy variable. A two-sided test of equality of the study drug (Traumed[®] gel) and the comparator (placebo) at level 0.05 based on an expected raw scale treatment difference of AUC 25 [mm x days] and a common standard deviation of AUC 75 [mm x days] for the response variables (re-expressed for nonparametric evaluation in terms of the Mann-Whitney statistic as $MW = 0.6$ (see section 11.1.3), achieves a power of at least 90% for parametric first line analysis as well as for second line nonparametric analysis if the sample size is set to 291 patients for the Traumed[®] gel group and to 146 patients for the placebo group.

Due to an additional safety requirement that AEs with incidence level of 1% for Traumed[®] gel are found during the study with probability 95%, 299 patients for the Traumed[®] gel group are required. Assuming a drop-out rate from the Safety Analysis Set of about 4% an amount of 312 randomized patients in the Traumed[®] gel group is needed. With an allocation ratio of 2:1:1 (Traumed[®] gel : diclofenac gel : placebo) 156 patients are obtained in the diclofenac gel and placebo group each, that is, a total of 624 patients with acute unilateral Grade 1 or Grade 2 sprain of the lateral ankle.

In order to ensure the pre-defined power of the trial for the trial objectives including the confirmatory test for non-inferiority (Traumed[®] gel compared to diclofenac gel), which is based on the Per-Protocol Analysis Set (PP), a sample size enhancement is introduced for compensation of:

- cases for whom maintenance of blinding procedures may have been compromised and, thus, are representing a major protocol violation (exclusion from PP analysis).

For compensation, the final sample size will be enhanced to 202 patients for the diclofenac and Placebo group each, and to 404 patients for the Traumed[®] gel group resulting in a new total of 808 patients. *(revised per Amendment to protocol version 3.0)*

12. Study Report and Publication Policy

An integrated study report in accordance with the ICH Harmonized Tripartite Guideline (E3) (Structure and content of clinical study reports) will be developed.

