Estimation of sample size is based on the primary efficacy variable area under the curve (AUC) for pain on passive movement as measured by the Visual Analog Scale from baseline to Day 4. A two-sided test of equality of the study drug (Traumed® gel) and the comparator (placebo) at level 0.05 based on an expected raw scale treatment difference of AUC 25 [mm x days] and a common standard deviation of AUC 75 [mm x days] for the response variables (re-expressed for nonparametric evaluation in terms of the robust Mann-Whitney statistic as MW = 0.6), achieves a power of at least 90% for parametric first line analysis as well as for second line non-parametric analysis if the sample size is set to 291 patients for the Traumed® gel group and to 146 patients for the placebo group. Due to an additional safety requirement that AEs with incidence level of 1% for Traumed® gel are found during the study with probability 95%, 299 patients for the Traumed® gel group are required. Assuming a drop-out rate from the Safety Analysis Set of about 4% an amount of 312 randomized patients in the Traumed® gel group is needed. With an allocation ratio of 2:1:1 (Traumed® gel: diclofenac gel: placebo) we obtain 156 patients in the diclofenac and placebo group each, that is, a total of 624 patients with acute unilateral Grade 1 or Grade 2 sprain of the lateral ankle.

Sponsor: Biologische Heilmittel Heel GmbH	Name of Medical Product: Traumed® Gel	Active Ingredient(s): Homeopathic preparation, containing herbal and mineral ingredients as described in the Clinical Study Protocol
EudraCT number: 2016-004792-50		Indication: Acute ankle sprain

In order to ensure the predefined power of the trial, a sample size enhancement is introduced for compensation of:

· cases for whom maintenance of blinding procedures may have been compromised.

For compensation, the final sample size will be enhanced to 202 patients for the diclofenac and Placebo group each, and to 404 patients for the Traumed® gel group resulting in a new total of 808 patients.

For more details see [protocol] sections 11.1.3 and 11.4. (revised per Amendment to protocol version 3.0)

Diagnosis and Inclusion Criteria:

The patients have to meet all of the following inclusion criteria:

- 1. Acute unilateral Grade 1 or Grade 2 sprain of the lateral ankle
- 2. >18 years of age
- 3. Legally competent male or female outpatient
- 4. Injury occurred within previous 24 hours before first treatment expected
- Signed Informed Consent

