The summaries of the efficacy parameters, the statistical analyses of the primary efficacy variable, and the statistical analyses of the secondary efficacy variables will be performed on the Full Analysis Set (primary set for evaluation of superiority of Traumed® gel versus placebo, secondary set for evaluation of non-inferiority of Traumed® gel compared to diclofenac gel), and on the PP set (primary set for evaluation of evaluation of non-inferiority of Traumed® gel compared to diclofenac gel, secondary set for evaluation of superiority of Traumed® gel versus placebo).

Missing values for all efficacy parameters will be imputed by the last observation carried forward (LOCF) approach. In addition, a last percentile carried forward approach (LPCF) will be performed as sensitivity analysis (see also [protocol] section 11.1.4). Further sensitivity analyses resulting from the blind review of the data will be provided in the final Statistical Analysis Plan.

All statistical tests will be two-sided with a significance level of α =0.05, unless specified otherwise. Where appropriate, statistical tests will be supported by presenting estimates and 95% confidence intervals for the respective treatment effects and differences between the treatment groups. These estimates and confidence intervals will be based on the respective statistical models used for the analysis.

Confirmatory analyses

- AUC for pain on passive movement in VAS from baseline to Day 4 (test for superiority, Traumed® gel versus placebo), Full Analysis Set (FAS)
- AUC for pain on passive movement in VAS from baseline to Day 4 (test for non-inferiority, Traumed® gel versus diclofenac gel), Per-Protocol Analysis Set (PP)

If the first *a priori* ordered test (superiority) shows statistical significance, the subsequent hypothesis (non-inferiority) can then be tested individually in a confirmatory manner according to the principle of *a priori* ordered hypotheses (for control of alpha using stepwise testing see [Maurer et al. 1995]).

Clinical safety will be addressed by assessing AEs, physical examinations, vital signs and as needed laboratory assessments in a descriptive manner.

Contract Research Organisation:	AMS Advanced Medical Services GmbH
	[name]
	[name]
	[contact]
	[contact]
Statistician:	idv Datenanalyse & Versuchsplanung
	[name]
	[name]/ Germany

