9.3 Evaluations and Endpoints – First Line Analysis

9.3.1 Primary Efficacy Variable

9.3.1.1 Operationalizations in Final Protocol

Primary Efficacy Variable

Area under the curve (AUC)* for pain on passive movement in Visual Analog Scale (VAS) from baseline to Day 4

Confirmatory Analyses

1. AUC for pain on passive movement in VAS from baseline to Day 4 (test for superiority, Traumed[®] gel versus placebo), Full Analysis Set. The null and alternative hypotheses for the comparison of Traumed[®] gel versus placebo can be formulated as follows:

H₀: $\mu_T = \mu_P$ H_A: $\mu_T \neq \mu_P$

H₀: Null hypothesis; H_A: Alternative Hypothesis; T: Test Treatment; P: Placebo Treatment; μ: mean of population (AUC)

2. AUC for pain on passive movement in VAS from baseline to Day 4 (test for non-inferiority, Traumed® gel compared to diclofenac gel), Per-Protocol Analysis Set (PP). For the comparison of Traumed® gel versus diclofenac gel the null and alternative hypothesis can be formulated as follows:

H₀: $\mu_{T} - \mu_{R} > 25 \text{ [mm x days]}$

H_A: $\mu_{\text{T}} \cdot \mu_{\text{R}} \leq 25 \text{ [mm x days]}$

 H_0 : Null hypothesis; H_A : Alternative Hypothesis; T: Test Treatment; R: Reference Treatment; μ : mean of population (AUC)

Hypothesis no. 1 (superiority) is based on the FAS analysis set, while hypothesis no. 2 (non-inferiority) is based on the PP analysis set. This way, both hypotheses are based on the more conservative data set.

If the first *a priori* ordered test (superiority) shows statistical significance, the subsequent hypothesis (non-inferiority) can then be tested individually in a confirmatory manner according to the principle of *a priori* ordered hypotheses (for control of alpha using stepwise testing see [Maurer et al. 1995]).

^{*}All AUC calculations will be based on actual time of measurement.

The confirmatory analyses will be performed using an analysis of covariance (ANCOVA) with baseline pain VAS as covariate. Due to the expected small number of patients per center, an additional inclusion of center as covariate will not be performed (see also EMA Guideline on adjustment for baseline covariates, section 4.2.3., EMA/295050/2013).

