9.3.1.2 Additional Operationalizations

- Visit 4 (Day 7) will be introduced as additional primary endpoint in the chain of a priori ordered hypotheses, leading to the following final sequence of confirmatory analyses:
 - 1. AUC for pain on passive movement in VAS from baseline to Day 4 (test for superiority, Traumed® gel versus placebo)
 - 2. AUC for pain on passive movement in VAS from baseline to Day 4 (test for non-inferiority, Traumed® gel compared to diclofenac gel)
 - 3. AUC for pain on passive movement in VAS from baseline to Day 7 (test for superiority, Traumed® gel versus placebo)
 - 4. AUC for pain on passive movement in VAS from baseline to Day 7 (test for non-inferiority, Traumed® gel compared to diclofenac gel)

If the preceding *a priori* ordered test shows statistical significance, the subsequent hypothesis can then be tested individually in a confirmatory manner according to the principle of *a priori* ordered hypotheses (for control of alpha using stepwise testing see [Maurer et al. 1995]).

Comment: The original endpoints at Day 4 remain unchanged (hypotheses no. 1 and no. 2), however Day 7 is introduced as additional primary endpoint in the chain of *a priori* ordered hypotheses (hypotheses no. 3 and no. 4). This addition is implemented as per BDRM decision in order to avoid lack of assay sensitivity at the early stage of the ankle joint injury (C1502_MTG_NOTES_BDRM_09MAR2021_20210324).

- Descriptive procedures will be performed according to section 9.1.
- For the analysis of covariance, in addition to the table with descriptive statistics and the
 analysis of variance of the covariate (test for homogeneity of the groups with respect to
 the covariate), the following results of the analysis of covariance will be generated:
 - Analysis of covariance of the full model (separate regression lines for each group) with the following information:
 - Test for parallelism and group difference at X₀ as an indication of group differences in case the regression lines are not parallel (for the hypothesis of parallelism a 10%-level will be applied).

- Model parameter: for each group, the point of intersection of the regression line, the slope and the adjusted mean value of X₀, the common mean value of the covariates for all groups.
- Analysis of covariance for the reduced regression model (a single regression line for all groups for the assumption that the regression lines are parallel), with the following information:

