 - Covariates (within), an indication of the significance and relevance of the covariate for the criterion.
 - Test statistic for adjusted group differences, correct also for groups of unbalanced size.
 - Coefficient of determination R² for the amount of variation of the criterion, which is explained by the covariate and the differences between the groups.
 - Model parameter: the y-intercept and slope of the regression lines (slopes are now necessarily identical because of the reduction of the full model), adjusted mean values for a common value X₀ of the covariate.
- The analysis of covariance of the full model will be used for the confirmatory approach (the reduced regression model is provided as supportive information only)
- Descriptive Procedures: TESTIMATE V6.5.14; PROC BASIC STATISTICS / SCIENCEGRAPH V4.9.39
- Test Procedures: TESTIMATE V6.5.14; PROC ANALYSIS OF COVARIANCE

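### The confirmatory ANCOVA pools one residual variance over arms of unequal size and plans no robust standard error, so its tests and intervals are calibrated only if the arms have equal spread

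*SAP*

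**What the plan says.** SAP 9.3.1.1 carries the model over from Protocol 11.1.3: "The confirmatory analyses will be performed using an analysis of covariance (ANCOVA) with baseline pain VAS as covariate". Centre is not in the model. SAP 9.3.1.2 then selects the version with one regression line per group: "The analysis of covariance of the full model will be used for the confirmatory approach". The common-slope version is supportive only. The intervals follow the model (SAP 6.1): "These estimates and confidence intervals will be based on the respective statistical models used for the analysis".

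The sample size in Protocol 11.4, repeated in SAP 6.1, rests on "a common standard deviation of AUC 75 [mm x days] for the response variables". Allocation is 2:1:1 for Traumed, diclofenac and placebo.

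SAP 9.3.1.2 lists the ANCOVA output: homogeneity of the covariate, parallelism, slopes, adjusted means and R². It contains no comparison of residual variances between arms and no Welch-type, arm-specific or heteroscedasticity-consistent standard error. It does not say whether one model is fitted to all three arms or a separate model to each pair. For the reduced model it lists this output: "Test statistic for adjusted group differences, correct also for groups of unbalanced size".

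**The concern.** Separate slopes free the regression lines but leave a single residual variance. When arms are the same size, a pooled variance is fairly insensitive to unequal SDs. Here one arm is twice the size of each of the others, so unequal SDs shift the standard error of a contrast. In a three-arm fit, the spread of the third arm also enters a comparison it does not belong to.

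Unequal spread is plausible. The VAS is bounded at 0, and a treatment that removes a share of the pain would shrink the SD along with the mean. That is a plausibility argument; neither document gives arm-specific SDs.

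At stake is the calibration of hypothesis 1 (superiority over placebo), which gates the whole ordered sequence, and of the non-inferiority interval that is compared with the margin of 25 mm x days.

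**Working it through.** **The plan's own figure.** Protocol 11.4 gives a difference of 25, SD 75, two-sided 0.05 and 291/146 patients. SE = 75·√(1/291 + 1/146) = 7.61; 25/7.61 = 3.29; power = Φ(3.29 − 1.96) = 90.8%. The stated power of at least 90% reproduces, so the sample size is not in question.

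**Inputs for the check.** Protocol 11.4 plans 808 patients. SAP section 8 removes 184 issue patients from the confirmatory analyses: 808 − 184 = 624. At 2:1:1 this is 312/156/156. The split of the remaining patients by arm is not given, so this is an assumption. The arm SDs below are also assumed. If baseline correlates equally with outcome in every arm, residual SDs scale by one common factor, which cancels from the ratios.

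**Formulas.** For Traumed (T) against comparator C:
- correct SE = √(sT²/312 + sC²/156)
- model SE = s_pooled·√(1/312 + 1/156)
- three-arm fit: s_pooled² = (312·sT² + 156·sD² + 156·sP²)/624
- two-arm fit: s_pooled² = (312·sT² + 156·sC²)/468
- two-sided error of a nominal 5% test = 2·[1 − Φ(1.96·ratio)], where ratio = model SE / correct SE.

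**One case in full.** T 62.5, diclofenac (D) 62.5, placebo (P) 75. For T−P the correct SE is √(62.5²/312 + 75²/156) = 6.97. In the three-arm fit s_pooled = 65.85, model SE = 6.46 and ratio = 0.926. In the two-arm fit s_pooled = 66.93, model SE = 6.56 and ratio = 0.942.

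| SDs T / D / P | Contrast | Three-arm ratio | Two-arm ratio |
|---|---|---|---|
| 62.5 / 62.5 / 75 | T−P | 0.926 | 0.942 |
| 62.5 / 62.5 / 75 | T−D | 1.054 | 1.000 |
| 75 / 62.5 / 75 | T−P | 0.961 | 1.000 |
| 75 / 100 / 75 | T−P | 1.093 | 1.000 |
| 75 / 100 / 75 | T−D | 0.887 | 0.911 |
| 100 / 75 / 75 | T−P and T−D | 1.050 | 1.098 |
| 75 / 100 / 100 | T−P and T−D | 0.956 | 0.911 |

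In error terms:
- Row 1: T−P non-coverage is 6.9% (three-arm) or 6.5% (two-arm) instead of 5%.
- Row 3: if Traumed equals placebo, hypothesis 1 has a two-sided error of about 6.0% (three-arm) or 5% (two-arm).
- Row 5: one-sided non-inferiority error is 4.1% (three-arm) or 3.7% (two-arm) instead of 2.5%.

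**General rule.** In a three-arm fit, the superiority interval is too narrow only if sP² > 0.4·sT² + 0.6·sD², and the non-inferiority interval is too wide only if sD² < 0.4·sT² + 0.6·sP². In two-arm fits the conditions are sP > sT and sD < sT.

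**Effect of a robust standard error.** The three-arm separate-slopes ANCOVA was simulated with pooled and HC3 standard errors.
- SDs 62.5 / 62.5 / 75 (12,000 runs): T−P non-coverage 6.4% pooled, 4.6% HC3.
- SDs 75 / 100 / 75 (4,000 runs): two-sided T−D error 8.5% pooled, 5.2% HC3.
- SDs equal at 75 (4,000 runs): T−P error 5.1% pooled, 4.9% HC3.

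**The case against.** Homoscedastic ANCOVA is a conventional choice, and nothing in the documents shows that the spreads differ. The descriptive output (SDs by treatment, boxplots, the Day 4 scattergram with regression lines) would make a gross difference visible. The assumed SDs are not the plan's. These points limit the size of the concern. They do not remove it, because no rule follows from what the displays show. The Wilcoxon-Mann-Whitney and van Elteren sensitivity analyses give no interval for the mean difference on which the margin is set.

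Three stronger readings are tempting, and the documents do not support them.

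- A reader might infer that unequal spread makes the superiority interval too narrow and the non-inferiority interval too wide. That pair needs placebo to be the more variable arm and, if the two active gels have equal spread, also a three-arm fit. A more variable diclofenac arm makes the non-inferiority interval too narrow instead. A more or less variable Traumed arm moves both intervals the same way.
- A reader might infer that the primary test has an inflated type I error. In the example above this arises only in a three-arm fit; in a two-arm fit with Traumed and placebo equally variable the test is exact. References in SAP 9.3.1.2 to each group and all groups fit a three-arm model but do not settle it, since the hypotheses are pairwise and use different analysis sets. Where the spread shrinks because Traumed works, hypothesis 1 is false, so the loss is interval coverage and not a false positive.
- A reader might take the remark on unbalanced groups as an error. It concerns only the supportive reduced model and is true under that model's equal-variance assumption.

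**Conclusion.** The confirmatory tests and intervals rest on equal spread across arms, under unequal allocation, with no robust standard error planned. The direction of any error cannot be read from the documents. Its size is modest under moderate differences: with SDs of 62.5 against 75, the standard error is about 4 to 7% off in the affected three-arm contrasts tabulated. It is larger if one comparator is clearly more variable: about 11% (three-arm) or 9% (two-arm) too small for non-inferiority at a diclofenac SD of 100.

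These figures assume a 312/156/156 split, the stated SDs and equal baseline correlation in each arm. This is a worthwhile, cheap improvement. It is not a demonstrated error in the primary result, and the planned sample size stands.

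**What to change.** In SAP 9.3.1.2, before unblinding:
- keep the ANCOVA and its adjusted means;
- state whether each confirmatory model is fitted to two arms or three;
- compute standard errors, tests and 95% confidence intervals for the Traumed-placebo and Traumed-diclofenac contrasts with HC3 or arm-specific residual variances, for all confirmatory hypotheses;
- note beside the remark on unbalanced groups that it assumes equal variances; nothing else there needs changing.

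The cost is about 0.5% in standard error if the SDs are equal. If the ANCOVA procedure in the named package cannot produce robust standard errors, a second validated procedure is needed, which is more work than a wording change.

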6.2 Schedule of Study Procedures

	Initial Visit Screening/Baseline	Treatm Visit 2	ent Visits Visit 3	EoT Visit Visit 4	Final Visit Visit 5
	Day 1	Day 2	Day 4 + 1 day	Day 7 +/- 1 day	Day 14 +/- 1 day
Informed Consent	X				, , ,
Inclusion/Exclusion Criteria	X				
Demographics	X				
Pregnancy test (if applicable)	X			X	
Medical history	X			NA.	
Time and grading of injury	X		1		
Height/Weight (BMI) ¹	X	2			X ¹
Physical examination including			3		
blood pressure and pulse	X				X
Randomization	X		*		
Dispense patient diary ²	X	8	X		
FAAM-ADL ³	X	X	X	X	X
Pain at rest by Visual Analog		K 1543	3 05454		2 222
Scale (VAS) ³	X	X	X	X	X
Pain on passive movement by Visual Analog Scale (VAS) ³	X	x	x	X	X
	X		*		
IMP tubes dispensed Investigational treatment	100.50	v	37	37	
Application of soft support	X	X	X	X	
(elastic bandage)	X	X	X	X (as required)	X (as required)
Rescue medication dispensed	X		X (if needed)	X (if needed)	
Diary reviewed		X	X	X	X
Diary returned			X		X
IMP tubes weighted			X	X	
Rescue medication reviewed		X	X	X	X
IMP tubes returned and sealed			*	X	
Rescue medication returned			3		X
Check use of other pain	49	47	120	**	
medication and record if any	X	X	X	X	X
Record previous/concomitant	X	X	v	X	v
medication	Λ	Λ	X	Λ	X
Record Adverse Events ⁴	X	X	X	X	X
Record use of arm crutches	X	X	X	X	X
Confirmatory check of grading			X		
Application of semi-rigid brace for Grade 2				X	X
Question to patients which treatment they assume to have received					X

¹ At Visit 5 (day 14) only the weight will be measured.

² The first patient diary will be collected on Day 4. The patient will receive second diary on the same day.

³ The time point of each visits/measurements of patients shall be ideally the same at each visit (+/- 1 hour). 4 Including adverse events observed at the site of administration of the IMP (lateral ankle).

6.3 Assessment of Efficacy

6.3.1 Primary Efficacy Parameter

Pain assessment on VAS for evaluating pain on passive movement

Ankle pain will be measured using a 100 mm VAS starting with no pain (0 mm) and ending with most severe imaginable pain the patient may imagine in relation to his/her ankle sprain (100 mm).

First the patients will be asked after 5 minutes rest to assess their pain themselves on a VAS scale for a secondary efficacy assessment (for details see [protocol] section 6.3.2).

Than while the patient is still at rest the investigator should perform 10° dorsal- and 30° plantar flexion on the injured ankle and the patients will assess their pain themselves on a VAS scale (primary efficacy assessment). The range of movement will be controlled by using a goniometer. It is very important that no lateral move of the ankle joint will be made. The pain to be assessed is the pain on passive movement.

To ensure a consistent assessment between investigators, investigators will be trained together at the investigator meeting.

The date and time of assessment will be recorded. Pain assessments should take place +/- 1 hour related to baseline at each visit for the individual patient, whenever possible.

